#### Advertising

Any advertisements used in recruitment of subjects must receive prior approval from the Sponsor and the IRB. A copy of the IRB-approved advertising and the documentation thereof must be provided to the Sponsor.

#### **Data Collection**

The Principal Investigator has the responsibility for ensuring that all source documents (i.e., study and/or medical records) and CRFs are completed and maintained according to the study protocol and are available at the site.

## Case Report Forms

The Sponsor will supply the paper and/or electronic CRFs/data logs to be used in this study. It is the responsibility of the Principal Investigator to maintain and submit accurate and timely CRFs to the Sponsor. All hard copy CRFs/data logs will be filled out legibly in ink.

All questions should be answered. For paper CRFs, if an entry requires correction, a single line will be placed through the entry so as not to obscure the original record, the corrected entry will be initialed and dated by the individual making the change, and a reason will be given for the change. There will be no whiteouts or erasures. For electronic CRFs, if an entry requires correction, the change is made directly to the CRF in the database, the user is prompted to provide a reason for the change, and the correction is logged in by an electronic audit trail.

#### 2011001

If, for any reason, the subject does not complete the study, an explanation will be entered on the Subject Accountability CRF. All data gathered on the subject prior to discontinuation will be made available to the Sponsor.

## Source Documents

The Principal Investigator has the responsibility for ensuring that all source documents (i.e., study and/or medical records) and paper CRFs are completed and maintained according to the study protocol. Any CRF used as a source document must be identified as such in the Investigator Notebook.

Study data collected electronically will be saved on a disk or other suitable electronic media and will be left at the site at the completion of the study.

## Protocol Amendments/Changes

Changes to the Protocol following Institutional Review Board (IRB) approval affecting the safety of subjects, scope/objectives of the investigation, or the scientific quality of the study will be documented as amendments. Such changes require the Sponsor, Principal Investigator, and IRB approval prior to implementation, unless immediate action is required to safeguard subject safety. Administrative/minor changes (e.g., typos, changes in the Sponsor personnel [excluding medical monitor], etc.) will be documented as revisions but do not have to be submitted as amendments unless required by the IRB. Any change in the Sponsor's monitoring staff, Clinical Trial Manager or Medical Monitor during the conduct of the study, will be reported to the Principal Investigator.

#### **Good Clinical Practices**

This study will be conducted in compliance with applicable sections of the US Federal Regulations governing informed consent (21 CFR 50), IRBs (21 CFR 56), study conduct (21 CFR 312) and the International Conference on Harmonization's Good Clinical Practice Consolidated Guidelines, [ICH-GCPs, as published by the FDA on 9 May 1997, Federal Register, Volume 62, Number 90 pages 25691-25709]). During the course of the trial, the clinical site will be monitored by the Sponsor (Clinical Trial Manager or designee) to ensure compliance with the Protocol, regulations and guidelines, adequacy of the equipment and facilities, and satisfactory data collection.

## Institutional Review

Prior to study initiation, the Principal Investigator must obtain institutional review and approval of both the Protocol and the consent form, in compliance with the US Code of Federal Regulations, Title 21, Part 56 or the ICH-GCPs Consolidated Guidelines, Chapter 3. The Principal Investigator will maintain any original authorization letter(s) and forwards copies to the Sponsor. IRB approval letters should include the study title, the Sponsor's study number, the address of the IRB, date of request, and the signature of the IRB chairperson/designate. Additionally, the letter must acknowledge that both the Protocol and consent form have been approved by the IRB, with notification of any changes required. The study will not begin until the Sponsor has received written confirmation of IRB approval. This IRB shall also review the investigation at least once a year during study execution. The Principal Investigator must notify the IRB when the study concludes.

#### Obligation of the Principal Investigator

Following completion of the study, the Principal Investigator shall submit a final report to the Sponsor describing the conduct of the study, deviations from planned conduct, early withdrawals and subject accountability, adverse events, and other information on study conduct.

#### **Record Retention**

The Principal Investigator must retain the subject identification codes, informed consent documentation, clinical materials inventory, CRFs, medical records and other source data for a minimum of 2 years after the last regulatory approval has been received or the discontinuation of the study. The Principal Investigator must receive written authorization from the Sponsor before destroying any study document. The Principal Investigator will make records available for inspection and copying upon the request of an authorized employee of a government authority or the Sponsor. In the event the Principal Investigator retires, relocates, or for any other reason withdraws from the responsibility for maintaining records for the period of time required, custody of the records may be transferred to another person who will accept responsibility for the records. Notice of such a transfer must be given in writing to the Sponsor.

## Study Medication Dispensing, Storage and Accounting

Study products will be stored in a secure area, under environmental conditions as required by label instructions and dispensed only under the authorization of the Principal Investigator. The storage condition shall be properly

#### 2011001

documented. Both the receipt and dispensation of all study products will be documented using forms provided by the Sponsor and additionally may be documented on suitable forms provided by the site. Study products will not be returned to the clinical site nor returned to the Sponsor following the trial.

## **Subject Consent**

The Principal Investigator or their designee will obtain written informed consent for each subject prior to participation in the study, per the US Code of Federal Regulations, Title 21, Parts 50.25 and 50.27 and ICH-GCPs, Chapter 4, subpart 4.8. All study procedures must be explained in non-technical terms in the informed consent form.

1. INTRODUCTION

The purpose of this analysis plan is to provide a detailed description of statistical analyses that will be performed to produce the clinical report for Study 2011001. Analyses specified here are pertinent to the objectives stated in the protocol.

2. STUDY OBJECTIVES AND DESIGN

This is a multicenter randomized, controlled, single-blind, 2-treatment, parallel group clinical trial to assess gingivitis and maternity outcomes in pregnant women who undertake an advanced daily oral hygiene program. Up to 750 subjects were to be enrolled to complete the study with a target population of approximately 600 evaluable subjects. Subjects were adult female volunteers with moderate-to-severe gingivitis who were in their late first trimester or early-to-mid second trimester of pregnancy (8-24 weeks of pregnancy).

Sufficient screening was conducted to enroll approximately 300 evaluable subjects at each of two study centers. After informed consent was obtained, the baseline measures were recorded and subjects were randomized to either: 1) an advanced oral hygiene regimen consisting of marketed rechargeable toothbrush, toothpaste, mouth rinse and floss plus oral hygiene education counseling (Regimen), or 2) regular oral hygiene with an anticavity toothpaste, regular manual toothbrush and floss (Control).

Separate randomizations were generated for each study site with approximately equal numbers of subjects randomized to both groups. Each randomization was balanced for history of pre-term birth, smoking status and number of bleeding sites.

Study-related evaluations were scheduled, where possible, as part of routine prenatal visits. Dental examinations were conducted at Baseline before study product assignment, and monthly thereafter for 3 consecutive months of study product use. Product distribution took place at the monthly visits or via shipment when the subjects were not present for the monthly evaluation. Adverse events were collected from examination and interview. Oral hygiene and prenatal knowledge and practices were assessed by survey at Baseline and Month 3 visit.

The monthly gingivitis endpoints were the primary outcome measure, with the Month 3 evaluation being the primary time point of interest. Maternity outcome data (gestational age, birth weight, etc.) were abstracted separately from medical records as secondary variables with gestational age being of most importance. An interim analysis of the primary and secondary outcomes was performed by an independent statistician, and the target population size was adjusted. An independent Data and Safety Monitoring Board has assessed study design, conduct and outcomes at prescribed intervals with respect to study integrity, subjects' safety and evaluability.

3. CHANGES TO THE DESIGN/PLAN

An interim analysis was planned in the protocol and was limited to sample size calculations based on the observed variability after the interim database lock on February 11, 2013. The database had *approximately* 184 total subjects who had delivery data (approximately 100 from UAB and 84 from Penn).

The final determination of treatment differences will be evaluated by the final and locked database without an adjustment in Type I error rate since the purpose of the interim analysis was only to re-estimate the sample size. No hypothesis testing or treatment difference information was obtained at the interim. Furthermore, the treatment code identity was not revealed to the statistician who carried out the analysis or to any study or Sponsor personnel, but it was available to the Data and Safety Monitoring Board (DSMB) if needed. The DSMB chose to remain blinded at the interim analysis stage.

On February 11-12, 2013 the interim study data was provided to a designated independent (off-site) statistician who was not involved in the study execution or its conduct. Additionally, the independent statistician was also not involved in the evaluability of the final data. The independent statistician received the treatment code via a secure transfer from another identified statistician not supporting this project.

Sample size calculations were carried out for the birth outcome endpoints, Gestational Age and Birth Weight. Subsequently, the projected sample size from these analyses (as well as the current sample size) was used to compute an expected difference between products for the gingivitis endpoint, Total Number of Bleeding Sites at Month 3. The subject populations used in these calculations included the following at both sites together and for each study site separately:

- **Evaluable subjects (N=163):** Subjects who were provided with a sufficient supply of study products to last through at least 2/3 (~67%) of the study participation duration, and had not violated any major protocol criteria. See Interim Analysis Evaluability memo for list of non-evaluable subjects for Birth Outcomes and/or Bleeding endpoint. If a subject did not present for the Month 3 visit, the gingivitis data was assumed to be missing. The evaluable populations were different for Birth and Gingivitis endpoints.
- **Intent-to-Treat subjects, ITT (N=188):** Subjects who were randomized and used the study products. For the Bleeding endpoint, we did not include those subjects graded by examiner #129 (at Baseline) at The University of Alabama, which were considered as having inaccurate Loe Silness measurements (e.g., *'instrument/examiner error'*).

The sample size calculations were performed on Gestational Age and Birth Weight using 80% power in 2-sided testing with Type I error rate of 5% in the statistical model specified below. The delta between the treatment products was assumed to be 3-5% (for Gestational Age) and 5-10% (for Birth Weight) of the Control group (group with lower average Gestational Age and Birth Weight values) adjusted mean, and the error term variance was estimated from the mean square error from the specified models.

Estimating gestational age to be 38.1 weeks for the control product means that a 2.5% difference between treatments results in 0.953 weeks (~7 days), and the 3% difference corresponds to 1.143 weeks (~8 days) while the 5% difference equals 1.905 weeks (~13.3 days). Using this data, the sample sizes per treatment group were calculated and presented below for the two populations using the MSE from the specified models:

GEST AGE % Diff Btwn Products	SAMPLE SIZE per GROUP	
	Evaluable	ITT
	Subjects	Subjects
2.5%	354	334
3%	246	232
5%	89	84

[figure not shown]
Estimating average birth weight to be 6.87 lbs for the control product among evaluable subjects the 5% difference between treatments results in 0.343 lbs while the 10% difference corresponds to 0.686 lbs. Estimating average birth weight to be 6.73 lbs for the control product among ITT subjects, the 5% difference between treatments results in 0.337 lbs while the 10% difference gives 0.673 lbs. Using this data, the sample sizes per treatment group were calculated and presented below for the two populations using the MSE from the specified models:

BIRTH WT % Diff Btwn Products	SAMPLE SIZE per GROUP	
	Evaluable	ITT
	Subjects	Subjects
5%	439	452
10%	110	114

For Bleeding Site Reduction at Month 3, the estimated detectible difference between groups that would lead to a statistically significant result was calculated using 80% power, 2-sided testing, 5% Type I error, projected sample size (per group) from Gestational Age calculations (above) and the mean square error from the gingivitis model.

GEST AGE % Diff Btwn Products	DETECTIBLE DIFFERENCE (n per group)	
	Evaluable	ITT
	Subjects	Subjects
2.5%	2.9 (n=354)	2.9 (n=334)
3%	3.4 (n=246)	3.5 (n=232)
5%	5.7 (n=89)	5.9 (n=84)

In addition to the above detectible differences for given sample sizes from the Gestational Age calculations, below is a power curve with different sample sizes and detectible differences.

Statistical Models for Interim Analysis

The statistical model to determine treatment differences for mean Gestational Age and mean Birth Weight was an analysis of covariance (ANCOVA) model with previous preterm (< 37 weeks) birth (Y/N), smoking during pregnancy (Y/N), mother’s weight at delivery (in pounds), Study Site, and Treatment (A/B).

The model carried out on reduction of Number of Bleeding Sites (Baseline minus Month 3) was an analysis of covariance (ANCOVA) with the baseline Number of Bleeding Sites as the covariate and also included Treatment, Study Site and Treatment by Study Site interaction as factors.

The outcome of the interim analysis could have resulted in early termination of the research due to unexpected safety findings (input provided by the DSMB), continuing the study with the planned sample size or adjusting the sample size. The outcome of this interim analysis resulted in an increase in the sample size of 150 additional subjects (75 per study site).

4.0 DATA MANAGEMENT/QUALITY ASSURANCE

Prior to statistical analyses, the following steps were taken to ensure the accuracy, consistency, completeness, and reliability of the data:

- Electronic database review,
- Data management quality control checks (edit checks), and
- Additional review by the clinical/contractors of 100% of data (clinical source to database) from a random sample of 5-10% of subjects at each site.

5.0. DATA COLLECTED AND EVALUABILITY

5.1 Demographic and Baseline Characteristic Measurements

The following general demographic variables were collected during this study: Age, Race, Marital Status, Education, Income, Employment and Insurance variables. Additional baseline obstetrical variables were collected: Last Menstrual Period, Estimated Delivery Date, In-vitro Fertilization, Date of first Ultra Sound and corresponding Gestational Age reading, Previous Pregnancy (full, preterm, abortions), Smoking Status during pregnancy, Alcohol Use during pregnancy, and Other drug use. Additional variables collected were the subject's height and weight at baseline and subject's weight at each monthly visit and at delivery. The subjects also took an oral hygiene questionnaire at the Baseline and Month 3 visits.

At Baseline each subject had a Loe-Silness Gingival Index exam taken, which was used to assess number of bleeding sites for inclusion into the study.

Gingival crevicular fluid, plaque bacteria and blood samples were taken at the Baseline visit and will be analyzed separately outside of this protocol by the study sites.

5.2 Gingivitis Evaluations

Löe-Silness Gingivitis Index (GI)

The Löe-Silness GI was used to evaluate the gingiva based on color, consistency, and bleeding on probing. The entire dentition, with the exception of the third molars, was evaluated. For each tooth, six gingival areas (distobuccal, buccal, mesiobuccal, mesiolingual, lingual, and distolingual) were evaluated using adequate light, a mouth mirror, and a periodontal probe. Prior to evaluation, the teeth and gingiva were air dried as required to provide adequate visibility. The probe was inserted about 1mm into the gingival sulcus and passed from interproximal to interproximal. One aspect (either facial or lingual) of each tooth in a quadrant was first "skimmed" and then graded before passing to the next quadrant. Each of the six tooth surfaces was given a score of 0-3. A subject's full mouth GI score was determined by summing the scores and dividing by the number of sites examined. Criteria for the gingivitis scores are as follows:

Score	Criteria
0	Normal gingiva.
1	Mild inflammation – slight change in color, slight edema. No bleeding on probing.
2	Moderate inflammation – redness, edema, and glazing. Bleeding on probing.
3	Severe inflammation – marked redness, edema. Ulceration. Tendency to spontaneous bleeding.
8	Tooth not scored.
9	Tooth missing.

Due to the nature of the measurement, the Löe-Silness GI assesses both inflammation and bleeding. Gingival bleeding is derived from the GI scores at each site by assigning the site's Bleeding Score to 1 if the GI score is either a 2 or 3, and assigning it a value of 0 if the GI score

is 0 or 1. The full mouth bleeding score is determined by summing the Bleeding Scores of all scored sites.

When the tooth was missing or it was non-gradable at the Month 3 visit then the corresponding tooth was excluded from the previous visits (including Baseline) whole mouth gingivitis score or number of bleeding sites calculation.

Probing Pocket Depth Measurements

Local supragingival scaling may have been administered as needed to allow periodontal probing. Periodontal pocket was measured with a periodontal probe using standard methods. For each tooth, six gingival areas (distobuccal, buccal, mesiobuccal, mesiolingual, lingual, and distolingual) were scored using adequate light, a mouth mirror, and a periodontal probe. Prior to scoring, the teeth and gingiva may have been air dried as required to provide adequate visibility. The probe was inserted to the depth of the pocket, and pocket depth was measured (in mm).

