## 4. Inclusion Criteria

In order to be included in the study, each subject must:

- provide written informed consent prior to participation and be given a signed copy of the informed consent form;
- be at least the age of legal consent;
- be between 8 and 24 weeks of pregnancy;
- have at least 20 natural teeth:
- have moderate-to-severe gingivitis during pregnancy, including at least 30 intraoral sites with evidence of marginal gingival bleeding.

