6.3 Gingivitis Endpoints

Null Hypothesis: There is no difference between treatment groups with respect to the mean gingivitis change from baseline when an adjustment is made for the respective baseline gingivitis score and other demographic parameters.

Alternative Hypothesis: There is a difference between treatment groups with respect to the mean gingivitis score change from baseline when an adjustment is made for the respective baseline gingivitis score and other demographic parameters.

Statistical analyses for gingivitis efficacy endpoint will be based on whole-mouth average Löe-Silness change from baseline scores (Baseline score minus post treatment score) and will be considered the primary variable, with Month 3 the primary time point of interest. An analysis of covariance (ANCOVA) will be performed to determine treatment differences on the whole mouth average gingivitis reduction scores with the baseline gingivitis score as the covariate and also including study site, treatment, and the interaction of site and treatment as factors in the model. The interaction of treatment with the covariate will also be assessed for significance. If the interactions are not significant at the 10% level then they will be eliminated from the final model.

Additionally, 95% confidence intervals will be generated on the treatment difference for the average change from baseline scores. Separate analyses will be performed for each visit. The within-treatment difference from baseline gingivitis score will also be tested versus zero for each visit using the adjusted means from the ANCOVA model

The same analyses will also be generated for the reduction of Total Number of Bleeding sites and Pocket Depth reduction from baseline at each visit.

Testing for normality of the gingivitis endpoints will be carried out using Shapiro-Wilk test and residual plots. For non-normal data, a transformation such as taking the natural log (e.g., Total Number of Bleeding Sites) will be implemented or a non-parametric analysis will be carried out.

In addition to the ITT and Evaluable populations, the GI analysis will be carried out on the Intent-to-Treat subjects without examiner #129 data.

Additional subgroups may be defined for analysis on the gingivitis data, such as the following:

- By Study Site
- Subjects who had the same examiner for Baseline exam as for their post-baseline exam
- Subjects with the highest (top 50%) and Lowest (lowest 50%) Number of Bleeding Sites at Baseline

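### SAP 5.2 matches teeth only backwards from Month 3, so some change scores compare different sets of teeth; the effect is small and one sentence would remove it

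*SAP*

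**What the plan says.** SAP 5.2 scores each visit on whatever was graded at that visit. For GI, "A subject's full mouth GI score was determined by summing the scores and dividing by the number of sites examined". For bleeding, "The full mouth bleeding score is determined by summing the Bleeding Scores of all scored sites", with no denominator. Code 8 ("Tooth not scored") is separate from code 9 for a missing tooth, so teeth that are present but ungraded were foreseen.

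The only rule that aligns teeth across visits is in the same section: "When the tooth was missing or it was non-gradable at the Month 3 visit then the corresponding tooth was excluded from the previous visits". It includes Baseline among those earlier visits and names the whole-mouth gingivitis score and the bleeding count. Protocol section 15 gives the same scoring and no matching rule.

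SAP 6.3 analyses change from Baseline separately at each visit, with Month 3 GI as primary, and tests each arm's adjusted change against zero. It then extends this to two further endpoints: "The same analyses will also be generated for the reduction of Total Number of Bleeding sites and Pocket Depth reduction from baseline at each visit". Under SAP 5.6.2 a woman may miss one post-baseline visit and stay evaluable for the others.

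**The concern.** A within-woman change is interpretable only if the same teeth are counted at both times. The SAP accepts this when it removes a Month 3-ungradable tooth from Baseline, but it applies the principle in one direction. Three situations are left open:

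- **(a)** A tooth is coded 8 at Baseline and graded at a later visit. It counts at that visit and not at Baseline.
- **(b)** A tooth is graded at Baseline and Month 3 but coded 8 at Month 1 or 2. It counts at Baseline and not at that visit.
- **(c)** A woman has no Month 3 exam. The trigger never applies, so none of her teeth are matched at Month 1 or 2.

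Part of such a woman's change then reflects which teeth could be graded. For the bleeding count, (a) can only look like worsening and (b) only like improvement. The within-arm tests against zero have no other arm against which the artefact could cancel. The rule also omits pocket depth, and it does not say whether the recalculated Baseline count feeds the check in SAP 5.6 that makes women with fewer than 30 bleeding sites non-evaluable.

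**Working it through.** **Inputs.** Six sites per tooth ("For each tooth, six gingival areas", SAP 5.2). At most 28 teeth, assuming a usual adult dentition ("The entire dentition, with the exception of the third molars, was evaluated"). At least 20 teeth, since each subject must "have at least 20 natural teeth" (Protocol section 4). GI difference 0.05, variability 0.185, 300 per group, at least 90% power, two-sided 5% (SAP 6.8). Bleeding detectable differences at 80% power (SAP 3). The share of women with an unmatched tooth is not given; 5%, 10% and 20% are assumed, with one tooth each.

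**1. The plan's GI figure.** Power = Φ(0.05 / (0.185 × √(2/300)) − 1.96) = 91.2%. The stated power of at least 90% is reproduced, which confirms that 0.185 is used as an SD.

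**2. SD of the bleeding change.** SD = difference / (2.80 × √(2/n)). The SAP's 2.9 at n=354 gives 13.8 and its 3.5 at n=232 gives 13.5. All six entries give 13.4 to 13.8. This is a residual SD, because the SAP used the model's mean square error.

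**3. One unmatched tooth, one woman.**
- Bleeding: 0 to 6 sites. The extreme is 6/13.5 = 0.44 SD.
- GI: with T teeth scored and d the tooth's mean score minus the mean of the other teeth, the shift is d/T. For d=0 it is zero. For d=0.5 it is 0.018 (28 teeth) to 0.025 (20 teeth). For d=1 it is 0.036 to 0.050, and 0.050/0.185 = 0.27 SD.

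**4. Example with no true change.** There are 28 teeth; 27 average 1.2, and one scores 2 at all six sites. Mean GI with that tooth is (27 × 1.2 + 2)/28 = 1.229; without it, 1.2.
- Ungraded at Baseline, graded at Month 3: Baseline minus Month 3 is −6 sites and −0.029 GI.
- Ungraded at Month 1 only: Baseline minus Month 1 is +6 sites and +0.029 GI.

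**5. Arm-level shift, worst case per woman** (6 sites; d=1 with 20 teeth), equal to share × shift:

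| Share affected (assumed) | Bleeding | GI |
|---|---|---|
| 5% | 0.3 sites | 0.0025 |
| 10% | 0.6 sites | 0.005 |
| 20% | 1.2 sites | 0.010 |

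**6. Noise if both arms are affected alike.** Added variance = s² × f × (1 − f), where s is the shift and f the share. At f=20%:
- GI: 0.05² × 0.2 × 0.8 = 0.0004, and √(0.185² + 0.0004) = 0.186. Power goes from 91.2% to 90.8%.
- Bleeding: 36 × 0.2 × 0.8 = 5.76, and √(13.7² + 5.76) = 13.9. The detectable difference at n=354 is 2.93, which still rounds to 2.9.

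**7. Imbalance needed to bias the treatment difference by 10% of the reference difference.**
- GI, bias of 0.005: the arms must differ in share affected by 0.005 × 20 = 10 percentage points (d=1, 20 teeth), or by 0.005 × 28/0.5 = 28 points (d=0.5, 28 teeth).
- Bleeding, bias of 0.29 sites: 0.29/6 = about 5 points at 6 sites per affected woman, or 0.29/2 = about 15 points at 2 sites.

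**The case against.** A reader might set the one-woman shifts (up to 6 sites, or 0.050 GI) beside the SAP's 2.9 to 3.5 detectable sites and its 0.05 GI design difference, and infer that the primary result is at risk. The documents do not support that. Those references are differences between group means, whereas a single woman's shift belongs against the SD between women. The 0.050 figure also needs one tooth to differ from all the others by a full index point, and nothing in the documents suggests that this is typical.

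A reader might also take the three gaps as equal threats to the primary test. They are not. Gap (b) touches only Month 1 or 2. In gap (c) the woman has no Month 3 change, and no imputation is described that would give her one. Only gap (a) reaches Month 3, and only through code 8, because a tooth already missing at Baseline stays missing.

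Three further points stand:

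- Examiners are blind to assignment (Protocol section 3), and nothing suggests that ungradable teeth differ by arm.
- The model adjusts for Baseline, so how much of the raw shift survives in the treatment comparison depends on the relation between Month 3 and Baseline, which the documents do not give. Steps 5 to 7 carry the shift at full size.
- Matching everything to Month 3 has a reason behind it: each woman keeps one Baseline value across visits.

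SAP 5.1 also implies that the original Baseline exam governs entry, so the 30-site ambiguity is small. None of this closes the gap in the rule or protects the within-arm tests.

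**Conclusion.** The concern holds as a minor defect. Followed as written, the SAP produces change scores on unequal sets of teeth in three identifiable situations, and nothing else in either document corrects this. The bleeding count is the most exposed endpoint. Primary Month 3 GI is exposed through one route only, and not at all when the tooth resembles the rest of the mouth. Under an assumed 20% of women affected at d=1 with 20 teeth, the cost is 0.4 percentage points of power. The arm-level shift in that case is up to 0.010 GI, or 1.2 sites if all six sites bleed, and it would distort the within-arm changes. A biased treatment difference would need the share of affected women to differ clearly between arms, for which the documents give no reason. The text of the rule is certain; the size rests on assumed frequencies, one tooth per affected woman and a 28-tooth maximum.

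**What to change.** Replace the matching sentence in SAP 5.2 with:

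*For each post-baseline visit, whole-mouth GI, number of bleeding sites and pocket depth, and the Baseline value paired with that visit, are computed only from teeth graded at both Baseline and that visit.*

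Add that the unmodified Baseline exam is used for the 30-site evaluability check. Otherwise, removing one tooth (up to 6 sites) could take a woman who entered with 30 to 35 sites below 30.

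This sets the artefact to zero at every visit, covers women with no Month 3 exam, brings in pocket depth and leaves the sample size unchanged. It costs one or two sentences and a programming change. SAP 5.5 places completion of the SAP before unblinding, so the change belongs before that point. The downside is that a woman's paired Baseline value can differ slightly from one visit's analysis to the next.
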